4.11.2.7 Analysis of TEAEs Leading to Death

A summary of AEs leading to death will be summarized by SOC, PT including the number and percentage of subjects experiencing events by treatment group.

[name] S.A	
Protocol RI-01-006	Statistical Analysis Plan

A separate summary of related AEs leading to death will be provided by SOC and PT including the number and percentages of subjects by treatment group.

A by-subject listing of TEAEs leading to death will be provided including date of death, primary cause of death and its AE preferred term.

4.11.2.8 Analysis of TEAEs by Overall Anti-Drug Antibodyresult

A summary of TEAEs based on categories of overall Anti-Drug Antibody(ADA) result at EOS/ET (positive or negative) will be provided by SOC, PT, including the number and percentage of subjects experiencing events by treatment group. Overall, ADA result is defined as (binding antibodies (BAb)) result status (positive or negative) at EOS/ET visit.

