- ^{20.} Samples for detection of BAb and NAb will be collected before the administration of study drug infusion on Day 1 and Day 22. Additional samples for detection of BAb and NAb will be collected prior to study drug infusion at Weeks 8 and 28, as well as at the visits of Week 44 and Week 52 (EOS/ET Visit).
- ^{21.} COVID-19 testing (RT-PCR, Rapid Antigen test or test with similar nature antigen test but no antibody test) to be performed as close as possible but no more than 4 days before first dose administration. COVID-19 testing may be repeated at the discretion of the Investigator. Subjects should be randomised only after negative COVID-19 test result.

2 Introduction

Rituximab is approved for use in B-cell non-Hodgkin's Lymphoma (NHL), chronic lymphocytic leukaemia, rheumatoid arthritis (RA) in combination with methotrexate in adults with moderatelyto severely-active RA who have inadequate response to one or more tumour necrosis factor antagonist therapies, and granulomatosis with polyangiitis and microscopic polyangiitis in combination with glucocorticoids.^{1,2} Rituxan[®] is the commercially available innovator reference product in the United States (US); MabThera[®] is the commercially available innovator reference product in the European Union (EU). In Japan the commercially available product is Rituxan[®]. The proposed rituximab biosimilar (hereafter referred to as DRL_RI) is being developed as a potential biosimilar to Rituxan[®] and MabThera[®]. Rituximab, the innovator reference product approved in the EU (MabThera[®]) will be used as the selected reference medicinal product (RMP) for all study sites participating in this protocol.

The term "biosimilar" refers to a biologic drug that is developed to be similar to an existing approved RMP. Biosimilars are intended to treat the same diseases as the RMP using the same dose and treatment regimen. Unlike generic versions of chemically-synthesised small molecule therapies, biosimilars are not structurally identical to their RMP. This is due to the purity, characteristics, and activity of a specific product being dependent on, and sensitive to changes in the process by which it was manufactured. Therefore, the aim is to create a product with no clinically meaningful differences between the proposed biosimilar and the RMP in terms of pharmacokinetics (PK), safety, immunogenicity, and efficacy.

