4.5 End of Study Definition

Subjects who complete the study or subjects who discontinue from the study early will attend an EOS/ET Visit. Subjects experiencing disease progression will discontinue study drug and attend the ET Visit, which is to be scheduled 8 weeks after the last dose of study drug administration. These subjects will then be contacted by telephone for information on survival, AEs, and concomitant medications (Section 4.5.1) every 8 weeks, for a total observation period of 52 weeks (Section 4.5.1). Subjects discontinued from study drug due to a reason other than disease progression will also attend the ET Visit scheduled 8 weeks after the last dose of study drug, and then will continue to attend scheduled tumour assessments (at which AE and concomitant medication information will also be collected) up to disease progression or Week 52, whichever occurs first, as described in Section 4.1.1.

End of Study/Early Termination assessments are as follows:

- 1. Clinical assessments will include the following: Physical examination (including weight), vital signs measurement (blood pressure, heart rate, respiration rate, and oral, axillary, or tympanic body temperature).
- 2. Serum pregnancy test (human chorionic gonadotropin [hCG]) for women of childbearing potential. Female subjects with documented history of hysterectomy, bilateral oophorectomy, medically confirmed ovarian failure, or screening follicle stimulating hormone (FSH) test demonstrating post-menopausal status are exempted from pregnancy testing.
- 3. ECOG performance status assessments.
- 4. Clinical laboratory tests: Blood and urine samples will be taken for haematology, coagulation, biochemistry, and urinalysis.
- 5. Serum LDH and β -2 microglobulin evaluation.
- 6. 12-lead ECG (local ECG equipment with ECG to be read locally by a medically qualified and experienced ECG reader at the study site).
- 7. Viral disease screening at the EOS Visit.
- 8. Tumour assessments (using a computed tomography [CT] scan and, where available according to study site standard of care, a fluorine-18-fluorodeoxyglucose positron emission tomography [[¹⁸F] FDG-PET] or PET-CT scan) based on central radiology review in accordance with the response criteria for malignant lymphoma.¹³
- 9. Samples for BAb and NAb will be obtained.

- 10. A pharmacodynamic sample will be obtained only in the subjects undergoing PK and pharmacodynamic assessments.

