6.2.3 Study Drug Administration

Study drug (DRL_RI or MabThera[®]) will be administered by i.v infusion using the escalating infusion rate in accordance with the EMA approved labelling for MabThera[®]. The infusion rate must be well controlled to reduce the incidence of serious IRRs.

Only qualified personnel who are familiar with procedures that minimise undue exposure to them and to the environment should undertake the preparation, handling, and safe disposal of study drugs.

The study drug infusion must be administered in the presence of the Investigator/medically qualified study site staff (to enable compliance), and in an environment where full resuscitation facilities are immediately available. Vital signs will be monitored every 30 minutes during the course of the treatment administration and at the end of infusion or more frequently as necessary.

The study drug will be administered at a dose of 375 mg/m^2 of BSA. Subjects will receive induction treatment consisting of weekly i.v infusions for 4 weeks, followed by maintenance treatment consisting of an i.v infusion every 8 weeks from Week 12 up to Week 36.

The instructions below should be followed in conjunction with the local product labelling if it differs from these instructions. An electronic infusion pump is required to be used.

- First Infusion (Day 1): Initiate infusion at a rate of 50 mg/hour. In the absence of infusion toxicity, increase infusion rate by 50 mg/hour increments every 30 minutes, to a maximum of 400 mg/hour.
- Subsequent Infusions: Initiate infusion at a rate of 100 mg/hour. In the absence of infusion toxicity, increase rate by 100 mg/hour increments at 30-minute intervals, to a maximum of 400 mg/hour.
- Subjects should be closely monitored for the onset of cytokine release syndrome. Subjects who develop evidence of severe reactions, especially severe dyspnoea, bronchospasm or hypoxia should have the infusion interrupted immediately. In all subjects, the infusion should not be restarted until complete resolution of all symptoms, and normalization of laboratory values relating to the infusion reaction. At this time, the infusion can be initially resumed at not more than one-half the previous rate. If the same severe adverse reactions occur for a second time, the decision to stop the treatment should be seriously considered on a case by case basis.

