4.2.2 General Categorical Data Presentation

Categorical data will be summarized in terms of the number of subjects providing data at the relevant time point (n), frequency counts and percentages.

Percentages will be presented to one decimal place. Percentages will be calculated using 'n' (the total number of subjects providing data at the relevant time point) as the denominator.

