4.10.1.3 Handling of Missing Data

Various approaches will be applied to handle missing data; main, sensitivity and supportive analyses will be performed to explore the robustness of statistical results for the primary efficacy endpoint, see Sections 4.10.2.2.3 to 4.10.2.3.

Analysis and descriptive summaries for other endpoints will be based on available observed data.

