4.11.2 Analysis of Adverse Events

All reported terms for AEs will be coded using the latest version of MedDRA version 21.1 or the latest. Before database lock the latest version of MedDRA will be used to code the AE terms for all study subjects. The US National Cancer Institute (NCI) Common Terminology Criteria for Adverse Events (CTCAE), version 5.0 (NCI-CTCAE version 5.0) will be used by investigator to assess the severity grade of all AEs.

For all AE tables, subjects will be counted once for each MedDRA PT and each SOC. Unless specified otherwise, AEs will be summarized in the alphabetical order of SOC and then decreasing frequency of PT within the SOC for the treatment group. If the frequency of PT within the SOC is tied, PT will be sorted alphabetically. Summaries by PT will be sorted by decreasing frequency according to the "DRL_RI" subject incidence.

TEAEs are defined as any AE occurring or worsening on or after the first dose of study treatment. AEs which are already present before the first study treatment and increase in severity after the first study treatment will be considered as TEAEs. Pre-existing AEs before the first study treatment with no increase in severity after the first study treatment will not be considered as TEAEs.

All treatment-emergent adverse events (TEAEs) will be summarized by SOC, PT and CTCAE grade, including the number and percentage of subjects experiencing events.

An overview of AEs by treatment group will be provided, including number of subjects experiencing TEAEs, drug related TEAEs, serious TEAEs, drug related serious TEAEs, TEAEs leading to discontinuation of study medication, drug related TEAE leading to discontinuation of study medication, TEAEs leading to death,. The summary will also be provided for subgroups age group (< $60, \ge 60$ years), gender and race.

Imputation of partial dates of AE record is described in Appendix 2 Partial Date Conventions.

[name] S.A	
Protocol RI-01-006	Statistical Analysis Plan

A by-subject listing of all AEs will be provided by treatment group and will include AE term (SOC, PT, and Verbatim term), start date/time and corresponding study day, end date/time and corresponding study day, severity, infusion related reaction (yes/no), relationship, action taken, outcome, seriousness including criteria of serious adverse event (SAE).

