4.11.9 Analysis of Immunogenicity Data

Immunogenicity data, i.e., ADA (binding antibodies (BAb)) and neutralizing antibodies (NAb) will be summarized and analyzed descriptively for each scheduled time point (baseline, Week 4, Week 8, Week 28, Week 44 and Week 52/EOS or ET):

- Number and percentage of subjects with ADA (binding antibodies (BAb)) results (positive or negative) by treatment group and visit; for positive subjects, titer values will be summarized.
- Number and percentage of subjects with NAb results (positive or negative) will be presented by treatment group and visit.

[name] S.A	
Protocol RI-01-006	Statistical Analysis Plan

A by-subject listing of immunogenicity data will be provided.

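### The TEAE-by-ADA table takes its 'overall' antibody status from the EOS/ET sample alone, so subjects positive earlier but negative at EOS/ET are counted as ADA-negative

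*SAP*

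**What the plan says.** SAP 4.11.2.8 plans a table of TEAEs by SOC and PT, by treatment group, in two antibody categories, positive and negative. The section ties the grouping to EOS/ET twice, the second time as a definition: "Overall, ADA result is defined as (binding antibodies (BAb)) result status (positive or negative) at EOS/ET visit".

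Sampling is wider than that. Protocol Table 1-1, footnote 20, takes BAb and NAb before the infusions on Day 1 and Day 22, and continues: "Additional samples for detection of BAb and NAb will be collected prior to study drug infusion at Weeks 8 and 28". It then adds Week 44 and Week 52 (EOS/ET). SAP 4.11.9 lists the same six time points.

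On timing, Protocol 6.2.3 gives maintenance treatment as "an i.v infusion every 8 weeks from Week 12 up to Week 36". Under Protocol 4.5, subjects who progress stop study drug and "attend the ET Visit, which is to be scheduled 8 weeks after the last dose of study drug administration"; those who stop for other reasons also have an ET visit 8 weeks after their last dose.

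The other planned displays are BAb and NAb counts by visit (SAP 4.11.9) and two listings: "A by-subject listing of immunogenicity data will be provided" and "A by-subject listing of all AEs will be provided by treatment group" (SAP 4.11.2). Neither document defines an any-time, treatment-emergent, transient or persistent ADA status.

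**The concern.** A status called overall would be expected to reflect all of a subject's post-baseline samples. This one reflects only the last. TEAEs are counted from first dose onward, so a subject whose antibodies were detected during treatment and had disappeared by EOS/ET takes the whole adverse event history into the ADA-negative column.

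Protocol Section 3 lists anti-rituximab antibodies, together with their relationship to other outcomes, among the secondary endpoints. SAP 4.11.2.8 is the only visible summary that relates ADA to a safety outcome. Infusion-related reactions are broken down by the risk index, tumour grade and region, but not by ADA. Protocol 9.4.4 uses ADA only as a possible covariate in the separate population-PK model. At stake, then, is whether the one planned display of TEAEs against antibodies puts subjects in the right category.

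**Working it through.** **Which samples count.** Post-baseline BAb samples are Day 22, Week 8, Week 28, Week 44 and Week 52/ET, which makes 5. The rule uses 1 of them.

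**Where that sample falls.**
- Infusions: Days 1, 8, 15 and 22, then Weeks 12, 20, 28 and 36, a total of 8.
- Completers: 52 - 36 = 16 weeks from last scheduled dose to the status sample. All 8 infusions precede it, as do the three post-baseline samples taken during the dosing period (Day 22, Weeks 8 and 28).
- Early stoppers: the ET visit is 8 weeks after last dose. The status is therefore not read at a common time after dosing.

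**How subjects are classified.**

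| Post-baseline BAb before EOS/ET | BAb at EOS/ET | Column in the table | Ever positive post-baseline |
|---|---|---|---|
| negative throughout | negative | negative | no |
| any | positive | positive | yes |
| positive at least once | negative | **negative** | **yes** |

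The third row is the defect.

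**How many subjects.** The plan states no figure to reproduce and gives no ADA rates. With N subjects, ever-positive rate q, and share f of those negative at EOS/ET, the number misplaced is N × q × f. N = 312 is the planned total (SAP 4.13.2). The values of q (5-15%) and f (10-60%) are assumptions.

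- Low: 312 × 0.05 × 0.10 = 1.56, about 2.
- High: 312 × 0.15 × 0.60 = 28.08, about 28.
- If only 90% have an EOS/ET result (assumed), N = 312 × 0.90 = 280.8, giving 280.8 × 0.05 × 0.10 = 1.40 to 280.8 × 0.15 × 0.60 = 25.27, about 1 to 25.

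**Effect on the two columns (N = 312).**
- Positive column at q = 10%: 312 × 0.10 = 31.2 ever positive. Removing 3.12 (f = 10%) leaves 28.08; removing 18.72 (f = 60%) leaves 12.48.
- Misplaced share of the negative column: 1.56 / (312 - 15.6 + 1.56) = 0.5% at the low end; 28.08 / (312 - 46.8 + 28.08) = 9.6% at the high end.

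**Effect on a displayed difference.** Assume TEAE rates of 40% in ever-positive subjects (transient or not) and 20% in never-positive subjects, a true gap of 20 points.
- q = 5%, f = 10%: negative column = (0.95 × 0.20 + 0.005 × 0.40) / 0.955 = 20.1%, gap 19.9 points.
- q = 15%, f = 60%: negative column = (0.85 × 0.20 + 0.09 × 0.40) / 0.94 = 21.9%, gap 18.1 points.

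On these assumptions the main cost is a thinner positive column, with only mild dilution of the contrast.

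**The case against.** The strongest reply is about weight. The table is descriptive, and no hypothesis, margin or decision uses it. The rule is disclosed and identical in both arms, so the comparison between products is distorted only if antibody persistence differs by arm, which nothing here shows. Earlier positives remain visible in the by-visit tables and can be matched to events through the listings. Protocol 9.4.6 promises only summaries by time point, and Section 3 does not name TEAEs, so this table is an SAP addition. An any-time status also has biases: longer follow-up gives more chances to test positive, and some events precede the first positive sample.

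Most of this is right and limits the reach of the point. It does not remove it. Listings let a reader reconstruct the relationship but do not summarise it, and the population-PK covariate does not concern TEAEs. Renaming the table as EOS/ET status would correct the label but leave no summary by earlier positivity. The drawbacks of an any-time status can be stated beside the table.

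Subjects with no EOS/ET result are not part of the case. SAP 4.2.2 sets percentage denominators as "the total number of subjects providing data at the relevant time point", which takes them out. SAP 4.10.1.3 points the same way ("Analysis and descriptive summaries for other endpoints will be based on available observed data"), although it sits under the efficacy heading and is weaker support for a safety table.

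**Conclusion.** The concern holds. Under the stated definition, any subject positive at Day 22 or Week 8, 28 or 44 and negative at EOS/ET is shown as ADA-negative with all TEAEs since first dose. This follows from the text and needs no assumption. The number affected does: about 2 to 28 of 312 under the assumed rates, with the true figure unknown. The consequence is limited to this table. The primary BOR analysis and the by-visit immunogenicity summaries do not change. The definition should be corrected because this is the only visible TEAE summary by ADA status and the data for a better one are already planned.

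**What to change.** In SAP 4.11.2.8, define a subject's overall ADA status as positive if any post-baseline BAb sample is confirmed positive up to the data cut of the report carrying the table. Show separately the subjects positive at baseline and those with no post-baseline result. Keep the EOS/ET result in the by-visit table of SAP 4.11.9.

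State two limits with the table: the chance of a positive result rises with length of follow-up, and some TEAEs come before the first positive sample. The table therefore stays descriptive.

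Two small clarifications belong with this change:
- Name the report that carries the table. At the Week 28 cut, subjects still in the study have no EOS/ET sample, so the present definition cannot classify them; a status defined up to the data cut can.
- Say that an ET sample mapped to a scheduled visit under SAP 4.2.6 still counts.

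The cost is SAP wording and programming. BAb is already collected and listed at every scheduled point, so no new sample or visit is needed.

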4.11.2.9 Analysis of Non-Serious AEs

A summary of the number of subjects with non-serious AEs which defined as all AE excluding SAEs. Other AEs with incidence by $PT \ge 5\%$ will be additionally summarized by SOC, PT and treatment group.

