8.1.1 Screening (Day -35 to -1)

Subjects will undergo a Screening Visit at least 0 days, but not more than 35 days prior to the planned first day of blinded study drug.

During the Screening Visit, subjects will be screened at the study site to confirm their eligibility for participation in the study. The Investigator or sub-investigator will discuss with each subject the nature of the study, its requirements, and its restrictions. Written and signed informed consent must be obtained from each subject prior to the conduct of any protocol-specific procedures.

Screening procedures and assessments will be as follows:

The assessments are suggested to be conducted in the following chronological order.

- 1. Completion of a COVID-19 related screening questionnaire.
- 2. Obtain Informed Consent using a written ICF from the subject in accordance with local regulations.
- 3. Register screening of the subject using the IWRS.
- 4. Review subject eligibility (inclusion and exclusion criteria) with central confirmation of histopathology.
- 5. Assessment of subject stratification status based on ^{CCI} criteria (^{CCI}), tumour grade, and geographical area.
- 6. Histological confirmation of diagnosis (subjects can be screened for the study based on a diagnosis of CD20-positive, low burden FL confirmed at the investigational site). Subjects must have sufficient tissue samples available for the central pathology review (obtained on or within 12 months prior to the screening date), and a centrally-confirmed diagnosis prior to being randomised.
- 7. Document medical and oncology history.
- 8. Document subject demographics.
- 9. Clinical assessments will include the following: Physical examination (including a thorough assessment of the lymph nodes, liver, spleen, height and weight), vital signs measurement (blood pressure, heart rate, respiration rate, and oral, axillary, or tympanic body temperature).
- 10. Serum pregnancy test (hCG) for women of childbearing potential. Female subjects with documented history of hysterectomy, bilateral oophorectomy, medically confirmed ovarian failure, or screening FSH test demonstrating post-menopausal status are exempt from pregnancy testing.
- 11. ECOG performance status assessments.
- 12. Clinical laboratory tests: Blood and urine samples will be taken for haematology, biochemistry, coagulation, and urinalysis.
- 13. Serum LDH and β -2 microglobulin evaluation.

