Any relevant observations (including laboratory data) made at the Screening Visit (prior to signing the ICF) are to be recorded as a pre-existing condition on the medical history page of the eCRF.

recorded as medical history, and those with no past history should be considered as an AE/SAE.

The following variables will be recorded for each AE: verbatim/AE description, time and date for AE start and stop, severity, seriousness, causality rating, whether or not the AE caused the subject to discontinue, and the outcome. A new AE must be recorded if the severity of the AE changes.

SAEs and AEs will be recorded starting after signing of informed consent until EOS Visit or in case of early termination until ET Visit or week 52, whichever occurs later (unless subject withdrew consent or lost to follow-up at or after ET). All SAEs and AEs have to be recorded, whether or not considered causally related to the study drug or to the study procedure(s).

When an AE/SAE occurs, it is the responsibility of the Investigator to review all documentation (e.g., hospital progress notes, laboratory, and diagnostics reports) related to the event. The Investigator will then record all relevant AE/SAE information in the eCRF. It is **not** acceptable for the Investigator to send photocopies of the subject's medical records to the Sponsor or Sponsor's designated safety services in lieu of completion of the AE/SAE in eCRF. There may be instances when copies of medical records for certain cases are requested by the Sponsor. In this case, all subject identifiers, with the exception of the subject number, will be blinded on the copies of the medical records before submission to the Sponsor.

The Investigator will attempt to establish a diagnosis of the event based on signs, symptoms, and/or other clinical information. In such cases, the diagnosis (not the individual signs/symptoms) will be documented as the AE/SAE.

In case the eCRF is down or unavailable due to technical difficulties at the site, the Investigator will use the back-up paper SAE form to report SAEs within 24 hours via fax or via email to the Sponsor's designated safety services. The paper SAE form and the contact details for reporting will be part of the site reference manual.

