4.11.2.1 Analysis of Pre-Treatment AEs

A pre-treatment AE is defined as any AE with an onset date before the date of first administration of study treatment.

A summary of the number of subjects with pre-treatment AEs by SOC, PT a including the number and percentage of subjects experiencing events will be provided.

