4.11.2.5 Analysis of TEAEs by Outcome

A summary of the number of subjects with TEAE outcome into "Not recovered/Not resolved", "Recovered/Resolved with sequelae/resolved with sequelae", "Recovering/Resolving", "Fatal", and "Unknown" categories for number of events by treatment group will be provided.

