4.11.3 Analysis of Deaths, Serious Adverse Events, and Other Significant Adverse Events

4.11.3.1 Analysis of Serious Adverse Events

Serious TEAEs will be summarized by SOC, PT including the number and percentage of subjects, number of events experiencing events by treatment group.

A summary of related serious TEAEs will be provided by SOC, PT including number and percentages of subjects experiencing events, number of events by treatment group.

A summary of the number of subjects with serious TEAE outcome into "Not recovered/ Not resolved", "Recovered/ Resolved", "Recovered/Resolved with sequelae/ resolved with sequelae", "Recovering/ Resolving", "Fatal", and "Unknown" categories for number of events by treatment group and overall will be provided.

A by-subject listing of SAEs will be provided.

[name] S.A Protocol RI-01-006

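### The non-serious AE table is not limited to treatment-emergent events, and the TEAE outcome table has no row for fully resolved events

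*SAP*

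**What the plan says.** **Non-serious events.** SAP 4.11.2.9 plans "A summary of the number of subjects with non-serious AEs which defined as all AE excluding SAEs". Its second sentence takes other AEs whose preferred term reaches 5% and says that they "will be additionally summarized by SOC, PT and treatment group". Neither sentence mentions treatment emergence, and the second does not say in which group the 5% must be reached.

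**When AEs are collected.** Protocol 8.4.2 states "SAEs and AEs will be recorded starting after signing of informed consent until EOS Visit". Under Protocol 8.1.1 the Screening Visit is "not more than 35 days prior to the planned first day of blinded study drug".

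**How the SAP separates events in time.** SAP 4.11.2: "TEAEs are defined as any AE occurring or worsening on or after the first dose of study treatment". SAP 4.11.2.1: "A pre-treatment AE is defined as any AE with an onset date before the date of first administration of study treatment", and these events get their own summary.

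**Outcomes.** SAP 4.11.2.5 sorts "TEAE outcome into 'Not recovered/Not resolved', 'Recovered/Resolved with sequelae/resolved with sequelae", followed by recovering, fatal and unknown. SAP 4.11.3.1 sorts "serious TEAE outcome into 'Not recovered/ Not resolved', 'Recovered/ Resolved" and then the same four remaining items, so the serious-event list has a separate item for events that resolved without sequelae.

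**The concern.** Two safety tables, programmed as written, would not show what a reader expects.

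In the first, events that began before any study drug are placed under a treatment arm, next to tables built on TEAEs. The serious and non-serious tables then rest on different event sets and do not add up to all TEAEs. The same pre-dose event is reported twice, once here and once as a pre-treatment AE.

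In the second, a TEAE that resolved completely has no row. The programmer must drop it, add a category the SAP does not list, or merge it with events that left sequelae. The all-TEAE and serious-TEAE outcome tables then cannot be reconciled.

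Comparing safety is a stated secondary objective (SAP 2.2), so these displays should be unambiguous even though they are descriptive.

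**Working it through.** The plan states no figure on this point, so there is none to reproduce. The check sets the definitions side by side.

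**Step 1: can a pre-dose event reach the 4.11.2.9 table?** Collection starts at consent (Protocol 8.4.2), and screening can open 35 days before dosing (Protocol 8.1.1). SAP 4.11 bases all safety analyses on the Safety Analysis Set, which SAP 4.4.3 defines as subjects with at least one dose. That removes subjects who were never treated. It does not remove earlier events in subjects who later were. Subtracting SAEs from all AEs does not remove them either. So the answer is yes.

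**Step 2: is this the plan's general approach?** No.

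| Section | Event set |
|---|---|
| Protocol 9.4.2, safety analysis | TEAEs |
| SAP 4.11.2, all events by SOC, PT and grade | TEAEs |
| SAP 4.11.2.1 | Pre-treatment AEs, on their own |
| SAP 4.11.2.2, terms at 5% or more in either arm | TEAEs |
| SAP 4.11.3.1, serious events | Serious TEAEs |
| SAP 4.11.3.3, events of special interest | Treatment-emergent and non-treatment-emergent, mostly shown separately |
| SAP 4.11.2.9, non-serious events | All AEs minus SAEs |

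SAP 4.14, which lists changes from the planned analysis, does not mention 4.11.2.9.

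**Step 3: what does it do to the percentages?** For one preferred term, let *a* and *b* be the post-dose incidences in the two arms and *p* the pre-dose incidence, which randomisation makes equal in expectation. Ignoring subjects who have the term in both periods, the table shows *a* + *p* and *b* + *p*. The difference is (*a* + *p*) − (*b* + *p*) = *a* − *b*, so it is unchanged. If a subject can have the term in both periods and is counted once, then under independence the difference is (*a* − *b*)(1 − *p*), which is close to *a* − *b* when *p* is small. The levels do rise, and a term can enter the 5% table when *a* is below 5% but *a* + *p* is not. The documents give no value for *p*, so I put no number on this.

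**Step 4: outcome categories.**

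| Outcome | Protocol 8.4.4 | SAP 4.11.3.1 (serious TEAEs) | SAP 4.11.2.5 (TEAEs) |
|---|---|---|---|
| Recovered/Resolved | yes | yes | **no** |
| Recovered/Resolved with sequelae | yes | yes | yes |
| Recovering/Resolving | yes | yes | yes |
| Not recovered/Not resolved | yes | yes | yes |
| Fatal | yes | yes | yes |
| Unknown | yes | yes | yes |
| Count | 6 | 6 | 5 |

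The with-sequelae item has the same doubled wording in both SAP lists, and 4.11.3.1 has plain Recovered/Resolved as well. The doubled item in 4.11.2.5 is therefore not the resolved category under another name. The resolved category is missing.

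**The case against.** The best case against the point is that it hardly matters.

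- The comparison of arms does not depend on 4.11.2.9. The all-TEAE table, the 5% TEAE table, the related-TEAE table and the serious TEAE table are all on the right basis. This stands, and it is why the point is minor.
- The section is titled for AEs, not TEAEs, and the by-subject listing gives start date and study day, so pre-dose events can be traced. This is true, but a reader of the summary table cannot separate them there.
- The split by arm is explicit only for the 5% sentence. This is correct, and the point is worded accordingly.
- The SAP uses AE loosely elsewhere: 4.11.2.7 is headed for TEAEs leading to death, yet its text speaks of AEs. The wording of 4.11.2.9 may be the same looseness. That is plausible, but this section gives an explicit definition, and a programmer would follow it.
- The missing outcome is probably a drafting slip. Every AE must be given one of six outcomes, so the data exist and the gap would be visible. I agree.

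A reader might go further and infer that pre-dose events dilute the contrast and so help a claim of similar safety. The documents do not support that. The AE sections plan counts and percentages, with no risk ratio, test or margin. Step 3 shows that the expected difference is unchanged when overlap is ignored. The only formal equivalence test is on best overall response (SAP 4.10.2.1). A reader might also infer that one arm is penalised. With equal expected pre-dose rates, neither is.

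**Conclusion.** Both parts hold as matters of specification, and both are minor. Followed literally, SAP 4.11.2.9 puts treated subjects' pre-dose non-serious events into a by-arm table and repeats what 4.11.2.1 reports. SAP 4.11.2.5 leaves one of the six protocol outcomes without a row.

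The reach is two descriptive safety tables. The primary analysis and the equivalence conclusion are unaffected.

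The first part assumes that the definition is applied as written and that some treated subjects have AEs between consent and first dose. The documents give no rate for such events, so the size of the effect on any term, or on which terms pass 5%, cannot be stated. The second part needs only a comparison of the three lists. It would be too strong to say that the outcome table will misstate how events ended, because the data are collected and the gap may well be caught in programming.

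**What to change.** - **SAP 4.11.2.9:** define the table as non-serious TEAEs, using the TEAE definition in 4.11.2, so that pre-existing events that worsen after dosing stay in. State the threshold as in 4.11.2.2: a preferred term at 5% or more in either treatment group. Leave pre-treatment events in 4.11.2.1.
- **SAP 4.11.2.5:** list the six outcomes of Protocol 8.4.4, with Recovered/Resolved and Recovered/Resolved with sequelae as separate rows, matching 4.11.3.1.

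The cost is two wording edits. No new data are needed, and no information is lost.
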